The proposed direct comparison of tango to treadmill training is critical as it will put these two emerging forms of therapy head-to-head in order to determine their differential effects on actual locomotor performance (Aim 1), on brain activity during imagined walking (Aim 2), and on resting state functional connectivity of the locomotor control network (Aim 3) in people with PD. The combination of neuroimaging with exercise interventions is novel and will fill important gaps in our knowledge regarding basic locomotor control in PD and the mechanisms by which different exercises might convey benefit with respect to locomotor function. Previous neuroimaging work in different populations, as well as prior work in PD examining the effects of either tango or treadmill training on locomotion, sets the stage for this exciting work. Our use of different interventions along with two different neuroimaging techniques makes for a powerful and multi-faceted approach that will yield an extremely rich data set capable of addressing multiple gaps in our current knowledge.

B2 Rationale for this Study

Effective treatment of locomotor dysfunction in PD is essential, as gait difficulty is an early and major contributor to disability. The proposed study will provide important insights into the effects of different modes of exercise on locomotor function in PD, filling current knowledge gaps and guiding future design and delivery of optimal exercise interventions. This work is innovative because it: 1) uses a community-based exercise approach, 2) examines dance as a novel form of exercise and directly compares it to traditional treadmill training and *stretching*, 3) tests participants OFF medication to allow more accurate assessment of disease severity, and 4) utilizes two distinct neuroimaging approaches, in conjunction with interventions, to explore potential mechanisms of the effects of exercise on both brain function and brain connectivity.

C Study Objectives

C1 Primary Aim

SPECIFIC AIM 1: To determine the effects of tango, treadmill training, and stretching (control) exercise on locomotor function and other aspects of PD. The primary variable for this aim is gait velocity. Additional gait variables of interest are stride

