Participants will be assessed during the week prior to starting the intervention (pre-intervention), the week following completion of the intervention (postintervention), and three months after completing the intervention (follow-up) (Figure 1). At the preintervention visit participants will be notified as to whether they were randomized to the tango, treadmill or stretching group. Randomization sequences will be generated a priori by an independent statistician. Prior to commencing exercise all participants will undergo a physical examination and will be required to complete an on medication screening graded exercise test per previously established protocols [44-46] in order to determine whether or not they can exercise safely. All groups will receive 12 weeks of exercise, meeting 3 times per week for one hour each session. The exercise groups will thus participate in 180 minutes of exercise per week, meeting the CDC guidelines for physical activity[17]. All groups will exercise in community-based group settings to ensure that participants have similar experiences with respect to social interactions associated with participating in a group exercise class. Participants will be assigned to groups using a process of stratified blocked randomization. Self-selected forward gait velocity measured at baseline will be used to stratify participants into three categories: <1.1 m/s, 1.1-1.3 m/s, and >1.3 m/s. These strata have been chosen based upon our preliminary data from 60 individuals tested OFF medication. The average velocity for this group was 1.2 ± 0.1 m/s (mean \pm SD). Thus the middle stratum includes individuals within one SD of the mean and the upper and lower strata include individuals more than one SD above or below the mean, respectively. Each stratum will be randomized to the 3 groups using a block size of 10 to ensure that there is no temporal bias and guarantee that the number of participants at each level of walking performance who enter each study arm is the same.

2.d Risks and Benefits

There are no identifiable legal, social, or psychological risks associated with participation in the proposed studies. The identifiable risks are minimal and we are aware of no alternative procedures that can provide the same information.

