Using PASS software (NCSS, LLC, Kaysville, UT), we have powered each aim based upon preliminary data. Our primary variable of interest in Aim 1 is gait velocity. Average forward gait velocity +/- SD was 1.2 +/- 0.1 m/s and average backward gait velocity was 0.6 +/- 0.1 in a sample of 60 individuals with PD (H&Y = 2.4 +/- 0.2) tested OFF medication in our laboratory over the past year for a different study. The study has been powered to be able to detect differences of 1 SD, or 0.1 m/s, which is equivalent to an effect size of 0.4. Changes of 0.1m/s or more in gait velocity have been reported previously following both tango [22-24] and treadmill training [8, 29, 61, 62]. With an effect size of 0.4, 27 participants per group will provide 89% power to detect differences between or within groups using two-tailed tests at a significance level of 0.05. Based upon additional preliminary data from our lab, we have determined that this sample size is also more than sufficient to adequately power our secondary variables in Aim 1 (MDS-UPDRS-III, mini-BESTest, PDQ-39).

Aims 2 and 3 have been powered based upon preliminary data from our lab and sources in the literature. For Aim 2, our preliminary data from controls before and after a single session of treadmill training indicate an effect size of 0.91 for change in beta weights using the cerebellum as an exemplar region (pre = -0.094 +/- 0.111, post = 0.418 +/- 0.116, Figure 9) during imagined forward walking. We recognize that responses in those with PD may be less pronounced than in controls and as such have used a very conservative effect size of 0.45, half the size of the effect observed in controls, for our power calculation. Our preliminary data from people with PD (n=8) imagining forward walking indicate a beta weight of -0.075 +/- 0.097, which is comparable to the value obtained from young controls at baseline. Utilizing the data from the sample with PD and an estimated effect size of 0.45, 18 subjects per group will provide 80% power to detect differences between groups and 88% power to detect within group differences.

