Significant findings of differential BOLD signal changes have been localized in PD populations during similar imagined walking MRI paradigms with a total of 12 PD participants per group [59], further supporting that our proposed sample size is likely adequate. For Aim 3, utilizing rs-fcMRI (Figures 7,8) to determine correlations between regions in the locomotor control network, we have powered the study to enable detection of differences in correlation coefficients of 0.1 (mean correlation = 1.0, SD = 0.1, p = 0.05, effect size = 0.44, per data from Wu et al. 2009 and our own preliminary data). We will have 80% power to detect between group differences and 88% power to detect within group differences with 18 subjects per group.

Based upon our previous intervention studies [23], we anticipate an attrition rate of approximately 15-20% due to dropouts or failure to complete the required minimum of 85% of classes. We also expect MRI related complications due to head motion in roughly 30% of tested individuals. This estimate is based upon our preliminary data from individuals with PD (Fig. 4, 5) where we lost 24% of scans due to head motion greater than 2mm of translation or rotation during a scan. As such, we will recruit 40 subjects per group to account for attrition and data loss due to head motion and still obtain the needed final sample sizes for each aim. For Aim 1 dropouts will be handled utilizing intent to treat analyses with the last observation carried forward. Dropouts will be excluded from analyses in Aims 2 and 3 as full imaging data are needed from two time points.

G2 Interim Monitoring and Early Stopping

The protocol will also be evaluated and the risk to benefit ratio assessed twice annually.

G3 Analysis Plan and Statistical Methods

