For **Aim 1**, we will employ a repeated measures ANOVA with group (tango, treadmill, and *stretching*) and time (pre-intervention, post-intervention, and *follow-up*) as factors to determine whether and how these interventions impact gait velocity, our primary variable for Aim 1. Similar analyses will also be performed for secondary variables of interest, including the MDS-UPDRS-III, mini-BESTest, and PDQ-39. *As a secondary analysis for gait velocity, MDS-UPDRS-III, and mini-BESTest, we will determine percent difference between OFF and ON medication values at pre-intervention and post-intervention time points and compare these difference values using RM ANOVAs with group and time as factors. (If prescribed medications change over the course of the study then levodopa equivalent daily dose will be included as a covariate in these analyses.) This will allow us to determine if response to medications was different before vs. after intervention and whether this effect differed between groups.* Analyses will be conducted using NCSS software (NCSS, LLC, Kaysville, UT). All imaging analyses will be conducted using Brain Voyager (Brain Innovation, Maastricht, The Netherlands) and custom written Matlab (MathWorks, Natick, MA) software. For **Aim 2**, we will apply random effects general linear model analysis using forward and backward imagined tasks as individual contrasts. A false discovery rate (FDR) correction will be used to compensate for multiple comparisons. BOLD signal changes within the previously specified regions of interest will be compared for pre- and post-intervention conditions. Additionally, the three groups will be compared to each other in the post-intervention condition using RFX ANCOVA. For **Aim 3**, we will use an independent component analysis (ICA) to examine the strength of the correlation coefficients for anatomical regions identified as part of the locomotor control network. The strength of these correlations before vs. after intervention will be compared via two-tailed RM ANOVAs with group and time as factors. Finally, we will correlate BOLD signal changes during the imagined walking tasks (Aim 2) and changes in connectivity (Aim 3) with changes in motor performance.

G4 Missing Outcome Data

For Aim 1 dropouts will be handled utilizing intent to treat analyses with the last observation carried forward. Dropouts will be excluded from analyses in Aims 2 and 3 as full imaging data are needed from two time points.

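### The Aim 1 repeated measures ANOVA does not credit the stratification on baseline forward gait velocity; adjusting for that baseline would correct this, with a small to moderate gain that depends on an unstated correlation

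*Combined protocol and SAP*

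**What the plan says.** Section C1 on Aim 1: "The primary variable for this aim is gait velocity". Section 2.c: "Self-selected forward gait velocity measured at baseline will be used to stratify participants into three categories", with cut-points at 1.1 and 1.3 m/s and blocks of 10. One stated purpose is to "guarantee that the number of participants at each level of walking performance who enter each study arm is the same".

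For the analysis, section G3 says "we will employ a repeated measures ANOVA with group" and time (pre-intervention, post-intervention, follow-up) as factors. The only covariate named for an Aim 1 analysis is levodopa equivalent dose. It is conditional on medication changes and belongs to the secondary OFF/ON analysis. That analysis uses a model of the same kind and is meant to show "if response to medications was different before vs. after intervention and whether this effect differed between groups", which suggests that group × time is the term of interest for the main analysis too.

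Section G4 adds: "For Aim 1 dropouts will be handled utilizing intent to treat analyses with the last observation carried forward". Section G1 states: "With an effect size of 0.4, 27 participants per group will provide 89% power to detect differences between or within groups using two-tailed tests", and "we will recruit 40 subjects per group to account for attrition and data loss due to head motion".

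**The concern.** Stratifying on the outcome's own baseline makes chance baseline differences between arms smaller than simple randomisation would. The group × time contrast is built on change from baseline, and its error term is computed as if those differences were unrestricted. The design therefore buys balance that the analysis does not use. At stake are standard errors and p-values for the primary variable that do not match their true sampling behaviour, although the baseline measurement that would correct this is already collected.

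**Working it through.** **Inputs.** From the documents: forward velocity mean 1.2 and SD 0.1 m/s (G1); cut-points at ±1 SD and blocks of 10 (2.c); 40 recruited per arm and 15–20% attrition (G1); last observation carried forward, LOCF (G4). Assumed: the correlation ρ between baseline and later velocity, which is not given, taken from 0.3 to 0.9; 20% lost at random with baseline carried to both later visits; normal data; each block of 10 split 3/3/3 plus one participant to a random arm, since 10 does not divide by 3.

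**The plan's own figure.** A one-way F test with three groups of 27 and f = 0.4 has noncentrality 81 × 0.16 = 12.96 on 2 and 78 df. Its power is 89.5%, which agrees with the stated 89%. That calculation uses no baseline correlation and no stratum.

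**Step 1: reported standard errors with equal correlation between visits.** In units of σ², the per-person variance behind the pre-to-post contrast is 2(1−ρ) for the planned model and 1−ρ² with a baseline covariate, so the standard error ratio is √[2/(1+ρ)]. With no treatment effect, carrying baseline forward in 20% raises the correlation to ρ* = 0.2 + 0.8ρ. For example, ρ = 0.5 gives ρ* = 0.60 and √(2/1.60) = 1.12.

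**Step 2: what stratification does to the true variance.** Cuts at ±1 SD leave 26.2% of the baseline variance within strata. With perfect stratum balance, the true variance of the planned contrast divided by the variance it reports is [(1+ρ*) + 0.262(1−ρ*)]/2. At ρ* = 0.60 this is (1.60 + 0.105)/2 = 0.85.

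| Assumed ρ | 0.3 | 0.5 | 0.7 | 0.8 | 0.9 |
|---|---|---|---|---|---|
| ρ* under LOCF | 0.44 | 0.60 | 0.76 | 0.84 | 0.92 |
| Reported SE, planned ÷ adjusted | 1.18 | 1.12 | 1.07 | 1.04 | 1.02 |
| Planned: true ÷ reported variance | 0.79 | 0.85 | 0.91 | 0.94 | 0.97 |
| Simulated cut in true sampling SD from adjusting | 7% | 4% | 3% | 2% | none |
| Simulated null size of 4-df test, planned v adjusted (%) | 3.1 v 5.2 | 3.3 v 4.5 | 4.3 v 5.1 | 4.6 v 5.3 | 5.1 v 5.3 |

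The third row assumes perfect balance. With blocks of 10 and 32 per arm without LOCF, the simulated ratios at ρ = 0.3/0.5/0.7/0.8 are 0.79/0.86/0.92/0.95, and about 1.0 once baseline is adjusted for. Without stratification the planned model's ratio is also about 1.0, so the mismatch comes from stratification.

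**Step 3: with real effects.** If the three arms improve by 0, 0.05 and 0.10 m/s, carried-forward participants show no effect and the gap narrows. Simulated 95% half-widths at ρ = 0.3/0.5/0.7/0.8 are 0.048/0.041/0.032/0.027 m/s as planned and 0.041/0.037/0.031/0.027 m/s adjusted.

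**Step 4: unequal correlations.** Take 0.7 between baseline and each later visit and 0.85 between post and follow-up, without LOCF. The pooled repeated measures error uses the mean correlation, (0.7 + 0.7 + 0.85)/3 = 0.75, and so charges 2(1−0.75) = 0.50 for a pre-to-post difference. The true value is 0.3² × 0.262 + (1−0.7²) = 0.534 with perfect stratum balance and 2(1−0.7) = 0.60 with none. The pooled error is now too small, by a factor of 1.07 to 1.20 in variance. A nominal 5% test of that contrast would run at P(|Z| > 1.96/√1.07) ≈ 5.8% to P(|Z| > 1.96/√1.20) ≈ 7.4%. A simulation of this setting gave 6.5%, against 4.6% for the adjusted model.

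**The case against.** The strongest reply is that nothing here is an error. Baseline is already in the model as a level of time, so group × time removes stable differences between people. Under equal correlations the test is valid and merely cautious. For the Hypothesis 1a pattern (gains of 0, 0.10 and 0.10 m/s), the planned LOCF analysis has simulated power of 96.7% at ρ = 0.3 and at least 99.5% from 0.5 upward, so few decisions would change. Much of the gap in reported standard error is the general advantage of baseline adjustment over change scores and would exist without stratification. All of this stands, and it limits the point to one of efficiency and calibration.

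It also stands that a model of post-intervention and follow-up values alone would drop the within-arm change that Hypothesis 1a describes and that G1 includes in its power statement. The fix has to keep that.

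The reply does not remove the mismatch. The stratifying variable is the outcome's own baseline, the planned error term does not credit it, and Step 4 shows that the direction of the error is not guaranteed to be cautious.

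A reader might infer more than the documents support:

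- That baseline is missing from the analysis. It is not; what is missing is its use as a covariate.
- That the treatment comparison is biased or the trial underpowered. Neither is shown, and the 89% does not rely on adjustment.
- That the planned confidence intervals are too wide. G3 specifies no intervals; the point concerns the standard errors behind its tests.
- That G3's silence on the deciding contrast, or G1's on which test the 89% describes, supports this point. Those are missing details and carry no weight here.

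**Conclusion.** The point holds as one of efficiency and calibration. The variable used to balance the arms is the primary outcome's baseline, and the Aim 1 model uses it only as a repeated outcome. With equally correlated visits, 40 per arm, 20% carried forward and no treatment effect, the reported standard error is about 18/12/7/4% larger than with baseline adjustment at ρ = 0.3/0.5/0.7/0.8, and 1 to 2% larger at 0.9. Null size is about 3% at ρ of 0.5 or lower. The true gain in precision is smaller: about 7/4/3/2% in sampling SD, and none at 0.9. With unequal correlations, the pooled error can be too small instead.

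The size rests on ρ, which the documents do not give, on reading group × time as the treatment test, and on the assumed dropout and block composition. The presence of the mismatch rests only on sections 2.c and G3.

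**What to change.** In G3, for the between-arm comparisons of forward gait velocity, fit the post-intervention and follow-up values on arm × visit with baseline forward velocity as a continuous covariate, or use an equivalent constrained longitudinal model with baseline adjustment. Report the between-arm difference at the post-intervention visit from that model. Fit it to the same LOCF data set, so that G4 need not change.

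Keep the repeated measures ANOVA time effects, or take within-arm changes from the longitudinal model, for the within-arm parts of Hypothesis 1a.

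Adjusting other Aim 1 outcomes, including backward velocity, for their own baselines is reasonable, but the gain there was not computed.

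The cost is SAP wording and one error degree of freedom. No new data or participants are needed.

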Hypothesis 2a: Following tango, a differential BOLD signal increase will be observed in the premotor area, supplementary motor area, and putamen during both imagined forward walking and imagined backward walking; following treadmill training, BOLD signal will increase in the primary somatosensory cortex and cerebellum during imagined forward walking, but not during imagined backward walking. No BOLD signal changes will occur in the stretching group.

Hypothesis 2b: *BOLD signal changes will be directly related to changes in actual locomotor performance.*

Hypothesis 3a: *Following tango, resting state functional connectivity of the premotor area, supplementary motor area, and putamen will increase; following treadmill training, resting state functional connectivity of the primary somatosensory cortex and cerebellum will increase. No changes will occur in the stretching group.*

Hypothesis 3b: *Changes in resting state functional connectivity of the locomotor control network will be directly related to changes in actual locomotor performance. No changes will occur in the stretching group.*

A3 Purpose of the Study Protocol

B Background

B1 Prior Literature and Studies

SIGNIFICANCE

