The potential risks to subjects are: a) effects of withholding overnight medication, b) loss of confidentiality, c) stumbling during locomotion, d) falling into the safety harness during testing on the treadmill, e) mechanical injury involving moving apparatus, f) Skin irritation from surface electrode preparation or rubbing of the electrodes on your skin during data collection may occur. g) fatigue associated with long periods of exercise and MRI

scanning, h) dizziness after the MRI, i) claustrophobic reaction to being in the MRI tube and j) effects of the loud noise generated by the MR scanning sequence.

We do not yet know the full extent to which exercise may benefit people with Parkinson disease. Recent evidence suggests that the benefits may include improvements in physical function as well as quality of life. This study will allow us to determine what the benefits may be and if different types of exercise have different benefits.

This project will be the first to directly compare tango to treadmill training and will explore the neurophysiologic changes in brain function and connectivity following these two different forms of exercise. The information gained will provide critical insights regarding the relative merits of the two exercise approaches for improving function in people with PD and add to our understanding of the potential mechanisms by which these interventions convey their respective benefits. If the three interventions both impart improvements in function and do so through very different effects on the brain, as hypothesized, this would suggest that both interventions are beneficial and that a combination of exercise might be more effective than either intervention alone as different aspects of locomotor control may be targeted. This could lead to future studies comparing different combination approaches to exercise rather than single mode exercise programs. Future work could examine the effects of different doses of exercise or different exercise intensities, the effects of long-term participation in exercise, and the retention of benefits through inclusion of follow-up evaluations. The imaging techniques proposed herein will also lay the groundwork to allow us to answer many other questions regarding locomotor control mechanisms in PD. The potential implications of this work are vast and the proposed study will set the stage for much future research.

2.e Early Withdrawal of Subjects

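### Hypotheses 2a and 3a claim that tango and treadmill act on different brain regions, but G3 specifies no group-by-region contrast, no forward-minus-backward contrast and no rule for combining regional results

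*Combined protocol and SAP*

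**What the plan says.** Section A2 states the hypotheses. Under 2a, after tango "a differential BOLD signal increase will be observed in the premotor area, supplementary motor area, and putamen" in both imagined directions, while "following treadmill training, BOLD signal will increase in the primary somatosensory cortex and cerebellum during imagined forward walking, but not during imagined backward walking". Under 3a the same regional split is carried over to connectivity: "following treadmill training, resting state functional connectivity of the primary somatosensory cortex and cerebellum will increase". The stretching arm is expected not to change. Section E2, 2.d draws a conclusion from the pattern: if the interventions improve function and "do so through very different effects on the brain, as hypothesized", a combination of exercises might do better than either alone.

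Section G3 gives the analyses.

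- Aim 2 uses a random-effects general linear model "using forward and backward imagined tasks as individual contrasts", with a false discovery rate (FDR) correction.
- Within arms, "BOLD signal changes within the previously specified regions of interest will be compared for pre- and post-intervention conditions".
- Between arms, "the three groups will be compared to each other in the post-intervention condition using RFX ANCOVA".
- Aim 3 uses repeated-measures ANOVAs on the strength of between-region correlations, with group and time as the factors.

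Region is not a factor in any of these models. Forward and backward imagery are not contrasted with each other. There is no rule for turning a set of regional results into a decision on 2a or 3a. The power statements in G1 cover a between-group and a within-group difference only.

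**The concern.** Hypothesis 2a is a claim about differences: between arms in their regional profile, and between forward and backward imagery in the treadmill arm. Hypothesis 3a makes the same regional claim for connectivity. Both are worded as changes within each arm, and the planned pre/post comparison follows that wording. Its natural reading is that a region significant in one arm and not in the other marks a difference between the arms. It does not: two arms with the same true effect will often fall on opposite sides of 0.05. The same applies to a significant forward contrast beside a non-significant backward one.

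What is at stake is the mechanistic conclusion of the trial. Without a named contrast and a decision rule, the regional pattern that counts as support would be chosen after the results are known.

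**Working it through.** **Inputs from the documents.** Three tango regions (premotor area, SMA, putamen) and two treadmill regions (primary somatosensory cortex, cerebellum), from A2. From G1: 18 per arm; effect size 0.45 for Aim 2 and 0.44 for Aim 3; 80% between-group and 88% within-group power; 40 recruited per arm; 15-20% attrition; scan loss of 24% observed and about 30% expected.

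**Assumptions, because the documents give no figure.** Standardised change per region 0.3-0.7 SD; correlation of change between regions 0.3-0.6 (0 to 0.8 as a sensitivity range).

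**1. The plan's own power.** Read the effect size as Cohen's f, with N = 3 × 18 = 54 and noncentrality λ = f²N.

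- Aim 3: λ = 0.44² × 54 = 10.45. Power is 80.9% on (2, 51) df and 88.7% on (1, 51) df, which reproduces 80% and 88%.
- Aim 2: λ = 0.45² × 54 = 10.94. Power is 82.8% and 90.0%, slightly above the stated figures.

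These are powers for one outcome at a time. None refers to a pattern across regions.

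**2. Equal effects in both active arms, read from separate pre/post tests.** Let p be the within-arm power, q = 1 − p, and take regions as independent. A given region is significant in its predicted arm only with probability pq.

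- At least one of five such regions: 1 − (1 − pq)⁵
- At least one in each set (two-way split): [1 − (1 − pq)³] × [1 − (1 − pq)²]
- All five: p⁵q⁵

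| p | one-way split | two-way split | all five |
|---|---|---|---|
| 0.50 | 1 − 0.75⁵ = 76% | 0.578 × 0.4375 = 25% | 0.1% |
| 0.80 | 1 − 0.84⁵ = 58% | 0.407 × 0.294 = 12% | 0.01% |
| 0.88 | 1 − 0.8944⁵ = 43% | 0.285 × 0.200 = 6% | 0.001% |

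Correlation lowers these figures. At 0.8 the one-way split is 70%, 48% and 33%, and the two-way split 5%, 2% and 1%.

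Simulation at correlation 0.3-0.6 and true change 0.3-0.7 SD gives a one-way split in the predicted direction in about 52-77% of trials, and a two-way split in about 4-18%. With Benjamini-Hochberg over five regions within each arm these become 35-73% and 1-9%. Under the same equal effects, the contrast proposed under the fix is significant in about 5% of trials.

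**3. What the planned between-arm tests can do.** Suppose each active arm changes only in its own set, and ask for significant tango-versus-treadmill differences of opposite sign, one named region per set, without FDR. Over correlations 0 to 0.8, power at 18 per arm is 10% to 1% at 0.5 SD, 28% to 16% at 0.7 SD and 63% to 59% at 0.955 SD. Allowing any region in each set raises this to 35% to 5%, 70% to 34% and 95% to 76%. Used this way, the tests give a false crossover in at most 0.5% of trials.

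**4. What the set contrasts add.** If one arm stands d above the other two, f = d√2/3 = 0.471d, so f = 0.45 means d = 0.45/0.471 = 0.955 SD, and half of that is 0.48 SD. Compare like with like: both set-level contrasts succeed (Holm), against at least one region per set passing a three-arm ANOVA with Benjamini-Hochberg.

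- At 0.955 SD: 92-97% against 83-88%.
- At 0.48 SD: 13-27% against 9-11%.

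**5. What the difference contrast cannot show.** With tango at 0.955 SD in its own set and treadmill without any effect, tango versus treadmill on the set difference is still significant in about 95-99.8% of trials. Requiring the treadmill set contrast as well limits a false claim of both halves to at most 0.05/2 = 2.5%, the chance of a two-sided 0.05 test being significant in the predicted direction under no effect.

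**The case against.** The strongest reply is that G3 does compare the arms directly, through the post-intervention ANCOVA in Aim 2 and the group-by-time ANOVA in Aim 3. This stands. A reader might infer from the missing region term that no planned test could show the dissociation. That goes too far: opposite-sign tango-versus-treadmill differences in the two sets would establish a crossover. What remains is that G3 does not name this reading, and that its power is low unless effects are near the planned size.

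A reader might also infer that a false dissociation is likely. The numbers support this only for a loose, one-way split. A false two-way split is uncommon to moderately common, and the complete five-region pattern occurs by chance in about 0.1% of trials or fewer.

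Nor should a large power gain be claimed. At 0.48 SD the single difference contrast has 96-99% power against 9-11% for the regional route, but the two criteria differ. The like-for-like gain is in step 4.

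Three further points stand. G3 does not say whether FDR is applied across regions or voxels, so the Benjamini-Hochberg figures rest on one reading. Aims 2 and 3 are secondary (C2). And 18 per arm is a minimum: G1's loss rates imply 40 × 0.80 × 0.70 = 22.4 to 40 × 0.85 × 0.76 = 25.8 usable pairs of scans per arm.

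**Conclusion.** The concern holds in this form. The region-by-arm claims of 2a and 3a and the forward-only claim of 2a have no pre-specified contrast and no combination rule, and the pre/post tests that match their wording are an unreliable basis for them. With equal true effects, a one-way split in the predicted direction arises in about 52-77% of trials (35-73% with Benjamini-Hochberg within arm), and a two-way split in about 4-18% (1-9%). These figures assume 18 per arm, 0.3-0.7 SD and inter-region correlation 0.3-0.6; the documents give neither of the last two. The change should be made before the imaging data are analysed. It concerns secondary aims and does not affect the gait velocity analysis.

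**What to change.** Add to G3:

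- **Aim 2, profile test.** For each participant, average the standardised pre-to-post change during imagined forward walking over premotor area, SMA and putamen, and separately over somatosensory cortex and cerebellum. Compare tango with treadmill on the difference of the two means (1 df, two-sided 0.05). This tests whether the regional profiles differ, and no more.
- **Aim 2, full dissociation.** Claim it only if two set-level contrasts also succeed, with Holm: tango versus the other arms on its set, and treadmill versus the other arms on its set.
- **Aim 2, forward only.** Compare the arms on the change in forward minus backward signal in the treadmill set. A non-significant backward test should not be offered as evidence for this claim.
- **Aim 3.** First state which connections belong to each set, and assign cross-set connections in advance. If the outcomes are pairs among the five named regions, 3 × 2 = 6 of the 10 pairs join the two sets, so averaging over a set has no meaning until this is done. Then apply the same profile and set-level contrasts.
- **Per-region FDR results.** Keep them as secondary, and state whether the correction runs over regions or voxels.

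No new participants or scans are needed. The cost is wording and some programming, with the set definitions for Aim 3 as the main work. There are two drawbacks. Averaging can blur an effect confined to one region, which the retained per-region results partly cover. And power for both set contrasts is modest, about 13-27%, at half the planned effect.
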